- g. In triplicate, 5 minutes (\pm 5 minutes) apart, before GEN3009 administration and 1-2 hours (\pm 15 minutes) after administration.
- h. All AEs must be reported from the first GEN3009 dose until 30 days after the last dose (refer to Table 6 for details on the safety follow-up visit). Medical conditions that occur after the ICF is signed and prior to first GEN3009 dose should only be reported as AEs if they were assessed by the investigator to be caused by a protocol-mandated procedure (ie, tumor biopsy and/or CT scan), including washout or discontinuation of prior medications.
- i. MRI/CT scan of the brain is mandatory during screening within 21 days of C1D1. Lumbar puncture is required only if clinically indicated and required within 21 days of C1D1.
- j. HIV testing is required at screening only if required per local health authorities or institutional standards
- k. At dose levels \geq [REDACTED] mg, the first dose of GEN3009 can be split into 2 consecutive days (ie, [REDACTED] mg at C1D1 and remaining amount at C1D2) after approval of the sponsor's medical monitor.

Table 11 Visit Assessment Schedule from Cycle 2 and Beyond – Expansion GEN3009 + GEN3013 (including Safety Run-in)

Treatment Cycle 28-day cycle	Section	Cycle 2-3						Cycle 4 -12	Cycle 13 and Beyond	Unscheduled	Treatment Discontinuation Visit ^a	Safety Follow- up Visit ^a	Survival Follow- up Visit ^b
Day		1d	4d	8d	11d	15d	22d	1d	1d	--	As soon as possible after withdrawn from treatment	60 days after last dose	Every 12 weeks after last dose
Visit Window		±2d		±2d		±2d	±2d	±2d	+7d		+7d	+14d	±14d
Body Weight	9.3.1	X		X		X	X	X	X	X	X		
Physical Examination (including lymph node assessment) ^c	9.3.1	X						X	X	X	X		
Neurotoxicity Syndrome Assessment	9.3.1.1	X		X		X	X	X	X	X	X		
Vital Signs	9.3.2	X ^d		X ^d		X ^d	X ^d	X ^d	X	X	X		
ECG (in triplicate)	9.3.3	X ^e		X ^e		X ^e	X ^e	X ^e		X ^e	X		
ECOG Performance Status	9.3.4	X						X	X	X	X		
Constitutional Symptoms	9.3.5	X						X	X	X	X		
Adverse Events ^f	10	X	X	X	X	X	X	X	X	X	X	X	
Concomitant Medication and Procedures	9.1.4	X	X	X	X	X	X	X	X	X	X	X	
Premedication & CRS Prophylaxis	6.2	X		X		X	X	X	X				
GEN3009 Administration	6.4.2	X		X		X	X	X					
GEN3013 Administration	6.4.2	X		X		X	X	X	X ^g				
New Anti-cancer Treatment												X	X
Survival Status	9.3.6											X	X
EFFICACY ASSESSMENTS													

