- e. In triplicate, 5 minutes apart (\pm 5 minutes), before GEN3009 administration and 1-2 hours (\pm 15 minutes) after administration. During Cycle 4 and for all subsequent cycles, ECGs are required at predose only. During an unscheduled visit, ECG is performed only if clinically indicated.
- f. All AEs must be reported from the first GEN3009 dose until 60 days after the last dose. If the subject initiates new anti-lymphoma therapy within 60 days of the last dose of GEN3009 and/or GEN3013, the safety follow-up visit should be performed prior to starting new anti-cancer therapy.
- g. After completion of Cycle 12, subjects who are in SD or better will have the option to continue receiving GEN3013 every 4 weeks until any discontinuation criteria is met.
- h. Refer to Section [9.2.2.1](#) for imaging requirements.
- i. Only for subjects with positive serology.
- j. Even cycles only.

Table 12 Visit Assessment Schedule for PK and ADA – Expansion GEN3009 + GEN3013 (including Safety Run-in)

Treatment Cycle: 28-day cycle	Section	Cycle 1									
		1d	2d	4d	8d	9d	15d	16d	18d	22d	23d
Predose (-30 min)	9.5, 9.6	ADA: 09 and 013 / PK: 09 only	PK: 09 only ^c		PK: 09 and 13		PK: 09 and 13			PK: 09 and 13	
Start of GEN3013 Injection +1 hour (+15 min)							PK: 13 only			PK: 13 only	
End of GEN3009 infusion ^a (+5 min)		PK: 09 only	PK: 09 only ^c		PK: 09 only		PK: 09 and 13			PK: 09 and 13	
End of GEN3009 infusion +2 hours (+1 hour)		PK: 09 only ^b	PK: 09 only ^c								
End of GEN3009 Infusion +24 hours (\pm 2 hours)			PK: 09 only ^b					PK: 13 only			PK: 13 only
End of GEN3009 Infusion +72 hours (\pm 24 hours) ^d				PK: 09 only					PK: 13 only		

Treatment Cycle: 28-day cycle	Section	Cycle 2									
		1d	2d	4d	8d	9d	15d	16d	22d	23d	
Predose (-30 min)	9.5, 9.6	ADA/PK: 09 and 13			PK: 09 and 13		PK: 09 and 13		PK: 09 and 13		
Start of GEN3013 injection +1 hour (+15 min)		PK: 13 only									
End of GEN3009 infusion +5 min ^a (+5 min)		PK: 09 and 13									
End of GEN3009 infusion +2 hours (+1 hour)		PK: 09 only									
End of GEN3009 Infusion +24 hours (\pm 6 hours)			PK: 09 and 13								
End of GEN3009 Infusion +72 hours (\pm 24 hours)				PK: 09 and 13							

Treatment Cycle: 28-day cycle	Section	Cycle 3	Cycle 4-12	Cycle 13 and Beyond	Unscheduled	Treatment Discontinuation Visit
----------------------------------	---------	---------	------------	---------------------	-------------	---------------------------------

Day		1d	8d	15d	22d	1d	1d		

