Visit Window			+2d	+2d	+2d	±4d	+7d		
Predose (-30 min)	9.5, 9.6	ADA/PK: 09 and 13	PK: 09 and 13	PK: 09 and 13	PK: 09 and 13	ADA ^c /PK: 09 and 13	ADA ^c		
Start of GEN3013 injection +1 hour (+15 min)									
End of GEN3009 Infusion +5 min ^a (+5 min)		PK: 09 only							
Unscheduled Visit								PK: 09 and 13	PK: 09 and 13

Note: Sample collection timing may be modified during the trial based on emerging data.

09=GEN3009; 13=GEN3013.

- a. After flush.
- b. Only in case of full infusion on Day 1.
- c. Only in case of split dose between Day 1 and Day 2.
- d. In case of split dose between Day 1 and Day 2, the Day 4 sample will be 48 hours after the complete infusion.
- e. Even cycles only.

Table 13 Visit Assessment Schedule for Biomarkers – Expansion GEN3009 + GEN3013 (including Safety Run-in)

Treatment Cycle: 28-day cycle	Section	Cycles 1 and 2										
		Screening	1d	2d	2d+2h	4d	8d	15d	16d	22d	22d+6h	23d
Visit Window							+2d	+2d		+2d	+8h	
Tumor Biopsy	9.7/ 9.8.2	X ^a	X ^{b,f}									
Cytokines	9.8.3.2		X ^c				X ^{c,d}	X ^{d,h}		X ^{c,d}	X ^d	X ^d
Complement	9.8.3.3		X ^c	X ^{d,i}	X ^{d,j}			X ^{c,d}	X ^d			
Immunophenotyping	9.8.3.1		X ^c	X ^{d,i}		X ^{d,j}	X ^{c,d}	X ^c		X ^{c,d}	X ^d	
PBMC	9.8.3.1		X ^c				X ^{c,d}	X ^{c,d}		X ^c		
Saliva DNA	9.8.3.4	X										
ctDNA/MRD Plasma	9.8.3.4/ 9.2.2.3		X ^c									

Treatment Cycle	Section	Cycle 3		Cycles 4-12	Unscheduled	Treatment Discontinuation Visit
		1d	15d	1d		
Day			+2d	±4d		
Visit Window						
Tumor Biopsy	9.7 /9.8.2					X ^b
Cytokine	9.8.3.2	X ^c			X	
Complement	9.8.3.3			X ^{c,e}	X	X
Immunophenotyping	9.8.3.1	X ^c	X ^c	X ^{c,e}	X	
PBMC	9.8.3.1			X ^{c,e}	X	X
Saliva DNA	9.8.3.4					

ctDNA/MRD Plasma	9.8.3.4/ 9.2.2.3	X ^c		X ^{c,g}	X	
---------------------	---------------------	----------------	--	------------------	---	--

a. Fresh lymph node biopsy (to be taken from patients with easily accessible lesions) or an archival lymph node biopsy (formalin-fixed paraffin-embedded, which is taken after most recent therapy prior to enrollment and taken within 6 months of Cycle 1 Day 1) is mandatory for lymphoma.

b. Unless otherwise agreed with sponsor's medical monitor or delegate, a fresh core biopsy is to be taken from patients with easily accessible lesions in Cycle 2 and at the End of Treatment visit.

c. If the visit occurs on an infusion day, the sample must be taken before IMP treatment(s) (-30 minutes).

d. Cycle 1 only.

e. Samples in even cycles only, starting Cycle 4.

f. Cycle 2 only.

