
Assess pharmacodynamic markers related to MoA of GEN3009 and GEN3013	
Pharmacodynamic markers in blood samples (leukocyte subset frequencies and phenotype, target antigen expression, complement regulatory protein expression, plasma complement levels and activation [CH50], and cytokine levels)

Table 20 Objectives and Endpoints for Expansion (GEN3009 + GEN3013 for R/R DLBCL)

OBJECTIVES	ENDPOINTS
Primary	
• Assess preliminary anti-tumor activity of GEN3009 + GEN3013 combination	• CR rate
Secondary	
• Further assess the preliminary anti-tumor activity of GEN3009 + GEN3013 combination	• ORR • DOR • TTR • PFS • OS • Rate and duration of MRD negativity
• Evaluate the safety and tolerability of GEN3009 + GEN3013	• Frequency and severity of AEs/AESIs/SAEs • Changes in laboratory parameters • Changes in vital signs • Frequency of dose interruptions, dose delays, and dose intensity
• Establish the PK properties of GEN3009 and GEN3013	• PK parameters: CL, AUC _{7days} , AUC _{last} , C _{max} , T _{max} , C _{trough} , and T _{1/2}
• Evaluate immunogenicity	• Incidence of neutralizing ADAs to GEN3009 • Incidence of neutralizing ADAs to GEN3013
Exploratory	
• Assess potential biomarkers predictive of clinical response to GEN3009 + GEN3013 combination	• Expression of CD3, CD20, CD37, and other markers in tumor biopsies before and during treatment • DNA mutation status and gene expression profiling (RNA-seq) in blood and malignant cells • ctDNA as response biomarker • Evaluation of immune populations, phenotype and function in tumors and blood
• Assess pharmacodynamic markers linked to efficacy and MoA of GEN3009 and GEN3013	• Pharmacodynamic markers in blood samples and within tumor (on-treatment biopsy) ((leukocyte subset frequencies and phenotype, target antigen expression, complement regulatory protein expression, plasma complement levels and activation (CH50), cytokine levels)

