9.6 Immunogenicity

Venous blood samples will be collected for measurement of serum concentrations of ADAs as specified in [Table 4](#) (Dose Escalation), [Table 7](#) (Expansion), or [Table 12](#) (Expansion Combination). In the Expansion Combination cohort, 1 sample each for GEN3009 and GEN3013 are to be drawn.

Samples should also be collected at the final visit from subjects who discontinued trial drug or were withdrawn from the trial. At visits where ADAs will be evaluated, 1 blood draw of sufficient volume can be used.

Each serum sample for ADA evaluation will be divided into 2 aliquots (one for ADA analysis and a back-up). Plasma concentrations of GEN3009 or GEN3013 will be analyzed (refer to Section 9.5) and those data will be used for interpretation of the ADA data.

The ADA samples may additionally be used to evaluate safety or efficacy aspects that address concerns arising during or after the trial period for further characterization of immunogenicity.

Samples may be stored according to local regulations at a facility selected by the sponsor to enable further analysis of immune responses to GEN3009 or GEN3013.

Genetic analyses will not be performed on these serum samples. Subject confidentiality will be maintained.

The detection and titer characterization of ADAs will be performed using validated, specific and sensitive Electrochemiluminescence Immunoassay (ECLIA) methods and the titer of confirmed positive samples will be reported. The analysis will be performed under the supervision of the sponsor at an assay CRO. Neutralization characterization of ADAs will be performed at sponsor laboratories using appropriate methods.

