11.1.4 Immunogenicity Analysis Set

The immunogenicity analysis set will include all subjects who receive at least 1 dose of trial drug and have a baseline and at least 1 evaluable on-treatment ADA sample.

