11.7 Immunogenicity of GEN3009/GEN3013

Immunogenicity analysis samples will be scored ADA positive or ADA negative and subsequently reported. From positive ADA samples, titer values and neutralizing antibody scores (positive or negative) will be determined and reported. ADA negative samples with drug on board above the drug tolerance limits of the ADA method will be scored inconclusive due to possible drug interference. The association between positive/non-positive ADA and PK (predose, AUC, C_{max}), major safety signals (CTCAE \geq Grade 3) and efficacy information (change in tumor size by CT scan) may be explored.

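### Table 12 (combination cohort) lists no ADA sample at treatment discontinuation, in conflict with Section 9.6 and Tables 4 and 7; if sites follow it, subjects who stop in Cycle 1 drop out of the immunogenicity set

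*Protocol*

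**What the plan says.** Protocol Section 9.6 refers to Table 4 (escalation), Table 7 (expansion monotherapy) and Table 12 (expansion combination) for ADA sampling, and then adds: "Samples should also be collected at the final visit from subjects who discontinued trial drug or were withdrawn from the trial". It does not exempt the combination cohort.

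Table 12 places ADA samples as follows:
- Baseline at Cycle 1 Day 1 predose: "ADA: 09 and 013 / PK: 09 only".
- First post-baseline sample at Cycle 2 Day 1 predose: "ADA/PK: 09 and 13". The same entry appears at Cycle 3 Day 1.
- From Cycle 4 onward, ADA is marked with a footnote, read here as "Even cycles only".
- At the Unscheduled and Treatment Discontinuation visits, PK for both drugs and no ADA.

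Tables 4 and 7 list ADA together with PK at both of those visits. Table 11 times the discontinuation visit as "As soon as possible after withdrawn from treatment", with a window of +7 days.

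Section 11.1.4 restricts the immunogenicity set to treated subjects who "have a baseline and at least 1 evaluable on-treatment ADA sample". Tables 19 and 20 make immunogenicity a secondary objective of the combination run-in and expansion, with one endpoint per drug, for example "Incidence of neutralizing ADAs to GEN3013".

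**The concern.** Sites usually draw blood from the schedule table. A site that follows Table 12 will take a PK sample at discontinuation but no ADA sample, although Section 9.6 asks for one and the other two schedules show it.

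Two things would follow. A subject who stops during Cycle 1 would have only a baseline ADA result and would not enter the set used for the secondary immunogenicity endpoints. A subject who leaves later would stay in the set, but ADA that developed after the last scheduled sample could be missed.

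The Cycle 1 losses may not be random. Some of these subjects would be leaving because of toxicity, and Section 11.7 proposes to explore ADA status against safety signals of Grade 3 or higher. Not every toxicity-related stop removes a subject, though. Section 7.4.2.2 allows GEN3009 to continue after GEN3013 stops, with the medical monitor's approval, and such a subject could still reach the Cycle 2 sample.

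**Working it through.** The plan states no sample size, precision target or dropout rate for immunogenicity, so there is no figure to reproduce. The check compares the schedules and then illustrates the size.

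**Step 1: the ADA entries side by side.**

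| Source | Unscheduled visit | Treatment Discontinuation Visit |
|---|---|---|
| Table 4 (escalation) | ADA with PK | ADA with PK |
| Table 7 (expansion monotherapy) | ADA with PK | ADA with PK |
| Table 12 (combination) | PK only | PK only |
| Section 9.6 text | not mentioned | ADA at the final visit after discontinuation or withdrawal |

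ADA is legible in the other Table 12 cells, so a damaged table is an unlikely explanation.

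**Step 2: planned ADA days under Table 12.** With 28-day cycles, Day 1 of cycle c falls on study day (c − 1) × 28 + 1. Through Cycle 12, for Cycles 1, 2, 3, 4, 6, 8, 10 and 12, this gives days 1, 29, 57, 85, 141, 197, 253 and 309. The gaps are 28 days up to Cycle 4 and 56 days after it.

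- A subject who stops before day 29 has only the day 1 sample and fails Section 11.1.4. By then the subject may have received four GEN3009 doses (Days 1, 8, 15, 22) and three GEN3013 doses (Days 8, 15, 22), per Table 21.
- A subject who leaves after Cycle 4 may have a last ADA sample up to about 56 days (8 weeks) old.

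**Step 3: illustrative size.** N is 20 for the combination expansion, and at most 32 with the run-in (12 + 20). The share d leaving before Cycle 2 Day 1 is an **assumption** of 5% to 20%. The calculation supposes that no site takes the Section 9.6 sample. Expected loss is N × d, and the chance of losing at least one subject is 1 − (1 − d)^N.

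| d | Expected loss, N = 20 | P(at least 1), N = 20 | Expected loss, N = 32 | P(at least 1), N = 32 |
|---|---|---|---|---|
| 5% | 1.0 | 64.2% | 1.6 | 80.6% |
| 10% | 2.0 | 87.8% | 3.2 | 96.6% |
| 20% | 4.0 | 98.8% | 6.4 | 99.9% |

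**Step 4: effect on precision.** If no subject is ADA-positive, the exact two-sided 95% upper limit for 0 of n is 1 − 0.025^(1/n).

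- N = 20: 16.8% for 0/20, rising to 17.6% for 0/19 (d = 5%) and 20.6% for 0/16 (d = 20%).
- N = 32: 10.9% for 0/32, rising to 11.6% for 0/30 (d = 5%) and 13.2% for 0/26 (d = 20%).

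The loss of precision is small. Who is missing matters more than the wider interval.

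**Step 5: would the added sample restore these subjects?** A subject who stops in Cycle 1 would then have a baseline and one post-dose sample. Whether that meets 11.1.4 depends on its counting as on-treatment, which the protocol does not define for this set. SAP Section 5.8 ends the on-treatment period 28 days after the last dose. That SAP is based on protocol version 4.0, and it covers neither the combination cohort nor an immunogenicity set.

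**The case against.** The strongest reply is that the body text already covers the point. Section 9.6 cites Table 12 and then adds the final-visit sample to whatever the tables contain, so a site reading the whole protocol would take it. This stands as a limit: the loss arises only where Table 12 is followed and 9.6 is not. It does not remove the conflict, and a schedule that omits the sample invites the omission.

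Three further replies also stand in part.
- Section 9.6 says final visit and does not name the Treatment Discontinuation Visit. Table 11 also has a safety follow-up visit at 60 days. Tables 4 and 7 make discontinuation the natural reading, but it is an inference.
- Section 9.6 asks for no ADA sample at unscheduled visits, so that part of the change rests only on consistency with Tables 4 and 7.
- The dropout range is assumed and is applied to the maximum cohort size.

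A reader might also infer that the missing sample is the one least affected by circulating drug, and that it is lost for every subject, because "ADA negative samples with drug on board above the drug tolerance limits of the ADA method will be scored inconclusive". The documents do not support this. Section 11.7 says how such samples are scored, not which visit has the least drug. The discontinuation visit is a prompt visit, not a washout visit. From Cycle 4 both drugs are given every 4 weeks and ADA is drawn predose, about 28 days after the previous dose, so a prompt discontinuation sample may carry more drug. Table 12 also keeps ADA sampling from Cycle 13, after GEN3009 has ended, for subjects who continue GEN3013.

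**Conclusion.** The conflict is real and minor. Table 12 disagrees with Section 9.6 and with Tables 4 and 7 about ADA sampling at treatment discontinuation in the combination cohort. If sites follow Table 12, subjects who stop before planned day 29 are left outside the immunogenicity set, and subjects who leave after Cycle 4 may have a last ADA sample about 8 weeks old.

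Under an assumed 5% to 20% stopping before Cycle 2 Day 1, about 2 to 6 of at most 32 subjects would be affected. That range rests on the assumed dropout, on the maximum cohort size and on no site applying 9.6.

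It would be too strong to say that early leavers will be excluded, since 9.6 asks for the sample, or that an inferential result is at risk. The endpoint is secondary, and Section 11.4.2 states that results are descriptive with no formal hypotheses. What is at stake is completeness and possible selection in the ADA summary.

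**What to change.** Three linked edits are needed:
- In Table 12, add ADA for GEN3009 and GEN3013 to the Treatment Discontinuation cell. For consistency with Tables 4 and 7, add it to the Unscheduled cell as well.
- In Section 9.6, state that the final visit means the Treatment Discontinuation Visit.
- In Section 11.1.4, state that this sample counts as on-treatment, and carry the same rule into the SAP when it is updated for the combination cohort. Without this, the table edit may leave the same subjects outside the set.

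The cost is two table cells, two clarifying sentences and a slightly larger blood volume. Blood is already drawn for PK at the discontinuation visit, and Section 9.6 allows a single draw of sufficient volume.

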9.7 Tumor Biopsy

During both Dose Escalation and Expansion, for subjects with accessible tumors, tumor samples are required for biomarker assessments. A fresh lymph node biopsy is preferable at screening and the biopsy can be a whole lymph node or core biopsy. A fine needle biopsy will not be sufficient. An archival lymph node tumor biopsy, which is the most recently collected lymph node biopsy after most recent therapy prior to enrollment, is also acceptable if taken within 6 months of C1D1 (Table 32).

During Expansion two fresh core tumor biopsies at C2D1 (\pm 1 week) for GEN3009 + GEN3013 cohorts and C2D15 (\pm 1 week) for GEN3009 monotherapy cohorts are mandatory for all patients with accessible tumors, where it is considered feasible without a high risk of complications for the patient based on the discretion of the investigator. Additionally, where feasible, a biopsy should be collected at the end of treatment visit. All tumor biopsies should be formalin-fixed, paraffin-embedded. Tumor biopsies will be examined as described in Section 9.2.2.3 and 9.8.2.

Table 32 Tumor Biopsy Collection During Dose Escalation and Expansion

Subject Diagnosis	Requirement
B-cell NHL, SLL or CLL	Fresh whole lymph node biopsy or fresh core tumor biopsies (2 cores) is required. If a fresh biopsy is not clinically feasible, an archival lymph node biopsy (FFPE) is acceptable, which is the most recently collected lymph node biopsy after most recent therapy prior to enrollment, if taken within 6 months of Cycle 1 day 1.

9.8 Biomarkers

Biomarker investigations in this trial will include safety markers, candidate predictive biomarkers, which may predict outcome to the treatment, and pharmacodynamic biomarkers. Biomarker assessments performed in the Dose Escalation and Expansion will focus on complement activation (primarily as pharmacodynamics marker), circulating cytokine levels (as safety assessment), CD37 versus membrane complement regulatory protein (mCRP) expression on leukocyte subsets (as candidate predictive markers for treatment efficacy), frequencies of (CD37-expressing) expressing leukocyte subsets (as pharmacodynamics markers for B lymphocytes expressing high CD37 levels,

and as safety assessment for other leukocyte subsets expressing lower CD37 levels), and activation marker expression on circulating immune effector cells (as potential pharmacodynamic marker). In the GEN3009 + GEN3013 Combination Cohort additional GEN3013 specific biomarker assessments will be added that will focus on T cell activation/exhaustion as potential safety and/or pharmacodynamic biomarkers and evaluation of CD3 and CD20 expression as potential predictive biomarkers for outcome to GEN3013 treatment. Additional biomarker assessments in the Expansion may be performed on tumor tissues and/or whole blood samples to expand on the understanding of MoAs of GEN3009 and GEN3013, predict subjects' outcome to GEN3009 monotherapy or GEN3009 + GEN3013 combination therapy, or deepen the understanding of CD37 and/or CD20 biology in lymphoma. All biomarker assessments will be performed at a central laboratory.

9.8.1 Sample Collections

Samples for biomarker analyses will be collected as specified in [Table 4](#), [Table 8](#), [Table 9](#), [Table 13](#), and [Table 14](#). Biomarker analyses are dependent upon the availability of appropriate biomarker assays and clinical response rates. Biomarker analysis may be deferred or not performed, if during or at the end of the trial, it becomes clear that the analysis will not have sufficient scientific value for biomarker evaluation, or if there are not enough samples or responders to allow for adequate biomarker evaluation. In the event the trial is terminated early or shows poor clinical efficacy, completion of biomarker assessments is based on justification and intended utility of the data.

Details on the collection, processing, storage and shipment of biomarker samples will be provided in separate documents (eg, sample handling sheets or laboratory manual).

